20.3 ADDITIONAL ENDPOINTS

For BCDVA, the frequency and proportion of eyes achieving each acuity line will be reported over time by IOL group. The proportion of investigational lens eyes achieving 20/40 or better at 6 months will be compared to the ISO SPE rate for posterior chamber IOLs (all first eyes) using a one-sided, exact test based on binomial distribution. The null hypothesis (based on the ISO guidance document) is that the proportion of investigational lens eyes achieving 20/40 or better BCDVA is greater than or equal to the ISO SPE values, and the alternative hypothesis is that the proportion of investigational lens eyes achieving 20/40 or better BCDVA is less than the ISO SPE values.

In addition, the mean LogMAR BCDVA will be compared between lens groups for first eyes using a non-inferiority method. The null hypothesis is that the mean difference (control minus investigational lens) between the control and investigational IOLs is ≤ -0.1 LogMAR (1 line) with the alternative hypothesis that the mean difference is > -0.1 LogMAR. A 90% confidence interval (CI) of a two-sample, two-sided, t-test will be used for evaluation.

For all other near endpoints, statistics similar to DCNVA described above will be used. In addition, the frequency and proportion of first eyes achieving each line will be reported over time by IOL group.

For intermediate endpoints, the mean LogMAR values will be analyzed similar to BCDVA described above. The frequency and proportion of first eyes achieving each line will also be reported over time by IOL group.

For defocus results, the defocus curve will be produced by IOL group. The diopters of defocus where the mean visual acuity 20/32 or better is achieved will be derived by visual inspection of the defocus curve.

For questionnaire data, including visual symptoms, the frequency and proportion of subjects with a given response will be reported by IOL group. For comparisons between IOL groups, Wilcoxon Rank-Sum test will be used for ordinal data, and Fisher's exact test will be used for categorical data. The null hypothesis is that there is no difference between responses, and the alternative hypothesis is that there is a difference between responses. Two-sided testing and alpha of 0.05 will be used to evaluate questionnaire data.

For contrast sensitivity data, descriptive analyses including mean, standard deviation, median, minimum, maximum and 90% confidence intervals will be presented by IOL group.

The frequency and percentage of medical findings, lens findings and non-directed ocular/visual symptoms will be reported over time by IOL group for both eyes.

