Consignments of all three study lenses will be supplied to the sites. All study lenses should be stored in the original packaging and kept in a dry place. Lenses should not be stored in direct sunlight or at temperatures greater than 45° C (113°F). Each lens is packaged in a lens tray and sealed in a peel-pouch. The lens is sterile as long as the package has not been opened or damaged and the shelf-life expiration date has not been exceeded. The Principal Investigator is responsible for ensuring that the investigational lenses are only used for subjects enrolled in this study.

COMPARISON CHART

Table 1 describes the dimensional and optical similarities between the study lenses and other associated AMO lenses.

Table 1: Comparison of Design Features

	SENSAR 1-PIECE IOL, MODEL AAB00 (MECHANICAL / MATERIAL PARENT)	TECNIS SYMFONY IOL, MODEL ZXR00 (OPTICAL PARENT)	MODEL ZHR00 (SUBJECT DEVICE)	MODEL ZQR00 (SUBJECT DEVICE)
LENS DESIGN	1-piece acrylic monofocal with spherical anterior surface	1-piece acrylic extended range of vision IOL with aspheric anterior surface		
LENS MATERIAL	Surface-treated SENSAR® soft acrylic material	Same as AAB00		
DIMENSIONAL FEATURES				
OVERALL DIAMETER	13.0 mm	Same as AAB00		
OPTICAL CENTER THICKNESS	0.74 mm (20 D lens)	0.66 mm (20 D lens)	Same as Symphony	
HAPTIC ANGLE	No angulation, but offset from optic body	Same as AAB00		
OPTIC BODY DIAMETER	6.0 mm	Same as AAB00		
HAPTIC MATERIAL	Same as optic	Same as AAB00		
HAPTIC WIDTH	0.39 mm	Same as AAB00		
HAPTIC THICKNESS	0.46 mm	Same as AAB00		
HAPTIC STYLE	C-Loop	Same as AAB00		
OPTICAL FEATURES				
OPTIC SHAPE	Biconvex	Same as AAB00		
ANTERIOR OPTIC PROFILE	Spherical	Aspheric	Same as Symphony	
POSTERIOR OPTIC PROFILE	Spherical monofocal	Diffractive EDF	Same as Symphony	Diffractive-refractive EDF
OPTIC EDGE DESIGN	PROTEC squared edge	Same as AAB00		
DIOPTRER POWER RANGE	+6.0 to +30.0D in 0.5D increments	+5.0 to +34.0D in 0.5D increments ¹	Same as Symphony ¹	
REFRACTIVE INDEX	1.470 (35° C)	Same as AAB00		
ADD POWER	N/A	N/A ²	N/A ³	
RANGE OF VISION	N/A	Through 2.0 D ²	Extended by between 0.25 D to 0.50 D compared to Symphony ³	

¹ Only IOLs from +16.0 D to +28.0 D will be used in the clinical study.

² There is no distinct add power. Clinically, the range of the defocus with binocular visual acuity above 0.2 LogMAR is approximately 2.0 D in the near direction.

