³ There is no distinct add power. Clinically, the range of the defocus with binocular visual acuity above 0.2 LogMAR is expected to be greater than 2.0 D in the near direction.

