Instructions for using the ETDRS near chart, including setting appropriate lighting conditions, and the visual acuity conversion chart between the number of ETDRS letters read and Snellen equivalents are provided in **Appendix H**.

The following near visual acuity measurements are to be performed per the visit schedule in **Appendix A**:

Test	Test Distance	Illumination	Type of Testing	Refraction Adjustment
UCNVA	40 cm	Photopic (85 cd/m ²)	Monocular Binocular	No adjustment
DCNVA	40 cm	Photopic (85 cd/m ²)	Monocular Binocular	-0.25 D added to ETDRS sphere Rx

DEPTH OF FOCUS TESTING (MASKED PROCEDURE)

Monocular, best corrected distance depth of focus testing will be performed at the 1-month visit on the first eye only for all subjects, and binocular best corrected distance depth of focus testing will be performed at the 6-month visit on all subjects.

Depth of focus testing will be performed under photopic conditions (85 cd/m², 80-110 cd/m² acceptable) using the M&S System at 4.0 meters with the ETDRS refraction in place (no adjustment necessary for test distance). The subject is to be defocused in -0.50 D increments with spherical minus lenses; at each defocus increment, a LogMAR measurement is obtained. Testing is to be conducted from +2.00 D through -4.00 D of defocus. Defocus curves will be generated for small (≤ 2.5 mm), medium (> 2.5 to < 4.0 mm), and large (≥ 4.0 mm) pupil sizes. Further instructions for defocus testing are detailed in **Appendix I**.

The following defocus curve measurements are to be performed per the visit schedule in **Appendix A**:

Test	Test Distance	Illumination	Type of Testing	Refraction Adjustment
Monocular Depth of Focus	4 m	Photopic (85 cd/m ²)	Monocular	No adjustment; ETDRS Rx only
Binocular Depth of Focus	4 m	Photopic (85 cd/m ²)	Binocular	No adjustment; ETDRS Rx only

TOLERANCE TO CYLINDER (MASKED PROCEDURE)

Binocular best corrected manifest cylinder defocus testing will be performed at the 1-month visit under photopic conditions (85 cd/m², 80-110 cd/m² acceptable) using the M&S System at 4.0 meters with the ETDRS refraction in place (no adjustment necessary for test distance). The subject is to be defocused in -0.50 D increments, from -0.50 D to -3.00 D of cylinder; at each cylinder defocus increment, a LogMAR measurement is obtained. Refer to **Appendix J** for further instructions.

PUPIL SIZE

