7.3 DEFOCUS

Best-corrected distance defocus testing will be performed at the 1- and 6-month visits (monocular at 1-month visit and binocular at 6-month visit). The mean visual acuity at each diopter will be plotted. The defocus curve will be presented for monocular and binocular by IOL model. The diopters of defocus where the mean visual acuity of 20/32

or better is achieved will be derived by visual inspection of the defocus curve. In addition, defocus curves will also be stratified by pupil size (\leq 2.5 mm, > 2.5 mm to < 4.0 mm and \geq 4.0 mm) for each IOL model. For binocular defocus curve, the average of the two pupil sizes will be used for stratification.

Binocular manifest cylinder defocus curve will be performed at the 1-month visits. The mean visual acuity at each diopter will be plotted. The defocus curve will be presented by IOL model.

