Monocular low contrast acuity (10%) DCIVA and BCIVA at 66cm (LogMAR) at 6M (N, Mean, SD, Median, Min, Max, 90% CI)	Х	Х	Х							
Monocular low contrast acuity (10%) DCIVA and BCIVA at 66cm by acuity line (No. and percent within each category)										
Add power for low contrast BCIVA (No. and percent)										
Visual Acuity – Distance										

ABBOTT MEDICAL OPTICS INC.

CONFIDENTIAL

	First Eyes	First Eyes	First Eyes	Second	Second Eyes	Second Eyes	Subjects	Subjects	Subjects	Comments
	ZHR00	ZQR00	Control	Eyes ZHR00	ZQR00	Control	ZHR00	ZQR00	Control	Comments
Monocular photopic UCDVA and BCDVA at 4 m (LogMAR) (N, Mean, SD, Median, Min., Max, 90% CI)	Х	Х	Х							
Monocular photopic UCDVA and BCDVA at 4 m by acuity line over time (No. and percent within each category)										
Binocular photopic UCDVA and BCDVA at 4 m (LogMAR) (N, Mean, SD, Median, Min., Max, 90% CI)							Х	Х	Х	
Binocular photopic UCDVA and BCDVA at 4 m by acuity line over time (No. and percent within each category)										
Defocus Testing										
Best-corrected monocular defocus curve overall and by pupil size (≤2.5 mm, >2.5 to <4 mm and ≥4.0 mm) at 1M	Х	X	Х							
Best-corrected binocular defocus curve overall and by pupil size (≤2.5 mm, >2.5 to <4 mm and ≥4.0 mm) at 6M							X	X	X	
Best-corrected binocular manifest cylinder defocus curve at 1M							X	Х	X	
Contrast Sensitivity										
Monocular contrast sensitivity testing overall and by pupil size (photopic: ≤2.5 mm, >2.5 to <4 mm and ≥4.0 mm mesopic: ≤4.0 mm, >4.0 to <=5.0 mm and >5.0 mm) (N, Mean, SD, Median, Min, Max, 90% CI) at 1M	х	Х	Х							
Binocular contrast sensitivity testing overall and by pupil size (photopic: ≤2.5 mm, >2.5 to <4 mm and ≥4.0 mm mesopic: ≤4.0 mm, >4.0 to <=5.0 mm and >5.0 mm) (N, Mean, SD, Median, Min, Max, 90% CI) at 6M							Х	Х	Х	
Refractive Outcomes										
Sphere, absolute cylinder and spherical equivalent (N, Mean, SD, Median, Min, Max)	Х	Х	Х	Х	х	Х				
Absolute spherical equivalent by diopter level (<=0.50, 0.51-1.00, 1.01-1.50, 1.51-2.00,>2.00) (No. and percent	Х	Х	Х	Х	Х	Х				

ABBOTT MEDICAL OPTICS INC. CONFIDENTIAL

	First Eyes	First Eyes	First Eyes	Second Eyes	Second Eyes	Second Eyes	Subjects	Subjects	Subjects	Comments
	ZHR00	ZQR00	Control	ZHR00	ZQR00	Control	ZHR00	ZQR00	Control	Comments
within each category)										
Absolute refractive cylinder by diopter level (<=0.50, 0.51-1.00, 1.01-1.50, 1.51-2.00,>2.00) (No. and percent within each category)	Х	Х	Х	Х	Х	Х				

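### The depth-of-focus range is read by eye from a group-mean curve with 0.50 D steps, with no interval and no difference from control (minor)

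*Protocol*

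**What the plan says.** Protocol 20.3 has the defocus curve produced by lens group and then states: "The diopters of defocus where the mean visual acuity 20/32 or better is achieved will be derived by visual inspection of the defocus curve". SAP 7.3 plots mean acuity at each defocus level by lens model and uses the same rule, that the range where mean acuity is 20/32 "or better is achieved will be derived by visual inspection of the defocus curve".

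Protocol 10.7 sets the grid: "The subject is to be defocused in -0.50 D increments with spherical minus lenses" and "Testing is to be conducted from +2.00 D through -4.00 D of defocus". Testing is monocular (first eye) at 1 month and binocular at 6 months.

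The size of effect the sponsor expects appears only in Table 1 of Protocol 7.1. For the control lens, footnote 2 says: "Clinically, the range of the defocus with binocular visual acuity above 0.2 LogMAR is approximately 2.0 D in the near direction". For the investigational lenses, the range-of-vision row reads "Extended by between 0.25 D to 0.50 D compared to" the control, and footnote 3 says the range with "binocular visual acuity above 0.2 LogMAR is expected to be greater than 2.0 D in the near direction".

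In SAP Appendix I the defocus rows list only curves, for example "Best-corrected monocular defocus curve overall and by pupil size". The near-acuity rows there list a 95% interval. The intermediate, distance and contrast sensitivity rows list a 90% interval.

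**The concern.** A value read by eye from a plotted mean curve depends on the reader. The plan gives no rule for reading between tested points and does not say who does the reading. It yields one number per group, so the result has no standard error and cannot enter the tests named elsewhere in the plan.

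The range still matters to a reader. Protocol Section 2 gives longer depth of focus than the control as the goal of both new designs. Protocol Section 4 says the study is meant to help choose a final design from two candidates. The synopsis and SAP Section 1 both list diopters of defocus among the other effectiveness endpoints. Without an interval, nobody can tell whether two lenses' ranges differ by more than chance unless they rebuild the precision themselves.

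**Working it through.** The documents state no power, SD or precision for this range, so there is no figure of theirs to reproduce. The check has two parts.

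**Does another clause fill the gap?**
- Protocol Section 20 and SAP 2.1 say each investigational lens is compared with control separately. They name no method that suits one eye-read value per group.
- Protocol 20.4 and SAP 2.3 give general descriptive statistics and say tests assuming normality will generally be used. A t-test needs a value per subject. N, mean and SD of acuity at each defocus level may be produced under these clauses. They do not give the precision of a crossing in diopters, which also depends on the local slope and on the correlation between levels within a subject.
- The notes to SAP Appendix I refer to the SAP text for inferential statistics. Section 7.3 has none for defocus.

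The gap is therefore real.

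**How large could sampling error be against the expected gain?**

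Inputs from the documents:
- Threshold: log10(32/20) = 0.204, about 0.2 LogMAR. By the SAP Appendix II formula, 75 letters gives (85 − 75)/50 = 0.20.
- Step: 0.50 D. Expected gain: 0.25 to 0.50 D, so 0.25/0.50 = half a step to 0.50/0.50 = one step.
- Control crossing about 2.0 D, so expected crossings are about 2.25 to 2.50 D. The lower one lies midway between the tested levels −2.00 and −2.50 D.
- n = 65 per group (Protocol 20.6).

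Assumptions:
- SD near the crossing 0.16 LogMAR. This is borrowed from the 1.6-line planning SD for monocular distance-corrected near acuity in Protocol 20.6, at 0.1 LogMAR per line. The range 0.10 to 0.20 is also shown.
- Slope of the mean curve at the crossing 0.1, 0.2 or 0.4 LogMAR per D.

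Formulas (delta method):
- One group: half-width = 1.96 × SD / (√65 × slope). With SD 0.16 and slope 0.2: 1.96 × 0.16 / (8.062 × 0.2) = 0.194 D.
- Difference: multiply by √2, giving 0.275 D.

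| Slope (LogMAR per D) | One group, SD 0.16 | Difference, SD 0.10 | Difference, SD 0.16 | Difference, SD 0.20 |
|---|---|---|---|---|
| 0.1 | 0.39 D | 0.34 D | 0.55 D | 0.69 D |
| 0.2 | 0.19 D | 0.17 D | 0.28 D | 0.34 D |
| 0.4 | 0.10 D | 0.09 D | 0.14 D | 0.17 D |

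The slope at which the half-width of the difference equals the gain is 1.96 × SD × √(2/65) / gain:
- SD 0.16: 0.0550/0.25 = 0.22 and 0.0550/0.50 = 0.11 LogMAR per D.
- SD 0.10 to 0.20: 0.14 to 0.28 for a 0.25 D gain, and 0.07 to 0.14 for a 0.50 D gain.

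**Does the proposed rule work?** It was simulated with 300 data sets of 800 bootstrap resamples each. The inputs were nine levels from 0.00 to −4.00 D, a control crossing at 2.0 D, a test crossing at 2.25 or 2.50 D, and an assumed split into between-subject SD 0.14 and within-subject SD 0.08. At slopes 0.1, 0.2 and 0.4 the half-width of the difference was 0.52, 0.26 and 0.13 D. Coverage of the 95% interval was 93% to 96%, and no resample ran past −4.00 D.

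**The case against.** The case against acting has five parts.

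- **Low consequence.** Depth of focus is one of the other endpoints in Protocol 6.3, without a success criterion or test. Protocol and SAP agree on the method. This stands, and it is why the point is minor.
- **The numbers show sampling error, not reading error.** This is also true. A careful reader would land close to the interpolated value. What interpolation adds is reproducibility and something that can be bootstrapped. The larger gain is the interval.
- **The design goal already has inference.** Distance-corrected near acuity at 40 cm is a 1/0.40 = 2.5 D demand, at the upper end of the expected crossings, and has a t-test and a 95% interval. Intermediate acuity at 66 cm (about 1.5 D) has a non-inferiority analysis. These show whether acuity differs near the end of the range. They do not give a range in diopters, which is the quantity the plan says it will report.
- **The magnitude rests on assumptions.** The differences run from 0.09 to 0.69 D, and a monocular planning SD is set against a gain defined binocularly. The figures therefore illustrate and do not prove imprecision. The gap in the plan does not depend on them.
- **A near-side rule may redefine the endpoint.** Neither Protocol 20.3 nor SAP 7.3 names a side, and testing starts at +2.00 D. The synopsis wording could even suggest a mean of per-eye values. However, the Table 1 footnotes define the range in the near direction at the same 0.2 LogMAR, and the analysis text uses only the mean curve. The near side is the reading the documents support, and it should be written down.

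**Conclusion.** The concern holds and is minor. The plan states a reader-dependent method for the depth-of-focus range and provides neither an interval nor a difference from control for it, while the acuity and contrast sensitivity rows of SAP Appendix I do list intervals. The expected gain is only half to one test step. If the SD near the crossing is 0.16 LogMAR, the 95% half-width of the difference exceeds a 0.25 D gain at slopes below 0.22 LogMAR per D, and exceeds a 0.50 D gain only below 0.11. At steeper slopes sampling error is smaller than the gain. SD and slope are assumptions; the absence of an interval is not. The clinical hypothesis and the primary analyses are untouched.

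**What to change.** In Protocol 20.3 and SAP 7.3, replace visual inspection with a stated rule:

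1. On the group-mean LogMAR curve, start at 0.00 D and move in the near (minus) direction.
2. Interpolate linearly between adjacent 0.50 D points to the first crossing of 0.2 LogMAR. Later re-crossings do not extend the range but stay visible on the plot.
3. If the mean at 0.00 D is already worse than 0.2, report 0 D. If there is no crossing by −4.00 D, report the range as beyond −4.00 D and give any difference involving it as a bound.
4. Give a 95% percentile interval by bootstrap of subjects within lens group, keeping all of a subject's defocus levels together and applying rules 1 to 3 in each resample. Do this for each group and for ZHR00 minus control and ZQR00 minus control, monocular at 1 month and binocular at 6 months. Label the results descriptive, with no test. The 95% level matches the near-acuity rows of SAP Appendix I.

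Add these results to the defocus rows of SAP Appendix I. Align the endpoint's name in the synopsis and SAP Section 1 with this definition. Keep the plotted curves, the 20/32 threshold and the group-mean basis.

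The cost is revised wording in both documents, a short program and slightly longer tables. No new data are needed, because Protocol Appendix I already has each subject's letter count recorded at every defocus level.

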20.4 VISUAL ACUITY CONVENTIONS AND GENERAL STATISTICS

Visual acuity data will be converted to LogMAR values prior to analysis and adjusted for the test distance used if it is not the standard distance for the chart. Descriptive statistics will typically include sample size (N), mean, standard deviation (SD), median, minimum (Min) and maximum (Max) as appropriate for continuous variables. For continuous variables, statistical tests (e.g., t-test) assuming normality will generally be used. For categorical data, the frequency and proportion will be reported and Fisher's exact test or Chi-square test will generally be applied. For ordinal categorical data, the frequency and proportion will be reported with the Wilcoxon Rank-Sum test generally used.

20.5 INTERIM REPORTS

Although interim study progress reports will be conducted for this study, all masking of study subjects and masked study technicians will be maintained and interim reports will not be disseminated to investigators/site personnel.

20.6 SAMPLE SIZE CALCULATIONS

For the primary endpoint of distance corrected near visual acuity, there is 90% power to detect a 1-line or greater difference in mean visual acuity between the investigational

lens groups and the control group (assume one-sided testing with an alpha of 0.025 and standard deviation of 1.6 lines) with 65 subjects in each lens group.

For contrast sensitivity there is 80% power to detect a non-inferiority margin of 0.15 log units between the investigational lens groups and the control group (assume one-sided alpha=0.05 and standard deviation of 0.34) with 65 subjects in each lens group.

If the dropout rate is assumed at 10%, approximately 73 subjects will be implanted in each lens group to achieve a minimum of 65 subjects in each lens group at 1 and 6 months.

APPENDIX A SUMMARY OF PROCEDURES REQUIRED AT EACH VISIT

Shaded lines indicate masked testing

Examination	Preop Both eyes	Op 1 st eye and 2 nd eye	1 day 1 st eye and 2 nd eye	1 week 1 st eye and 2 nd eye	1 month Both eyes	6 months Both eyes
Informed consent, ocular history, inclusion/exclusion criteria ^a , potential visual acuity, targeted refraction, IOL power calculations, biometry and randomization if required	X					
Lens power/serial number (masked)/operative procedures		X				
Manifest refraction (Snellen preop; ETDRS postop)	X			X	X	X
UCDVA - photopic, monocular (Snellen preop; ETDRS postop) ^c	X			X	X	X
UCDVA - photopic, binocular (ETDRS)					X	X
BCDVA - photopic, monocular (Snellen preop; ETDRS postop) ^c	X			X	X	X
BCDVA - photopic, binocular (ETDRS)					X	X
UCIVA and DCIVA - photopic, monocular at 66 cm (ETDRS) ^c					X	X
UCIVA and DCIVA - photopic, binocular at 66 cm (ETDRS)					X	X
UCNVA, DCNVA, BCNVA - photopic, monocular at 40 cm (ETDRS) ^c					X	X
UCNVA and DCNVA - photopic, binocular at 40 cm (ETDRS)					X	X
DCIVA and BCIVA, monocular, low contrast acuity (10%) ^c						X
Defocus testing, monocular ^c (M) and binocular (B)					M	B
Tolerance to cylinder testing, binocular					X	
Contrast Sensitivity testing, monocular ^c (M) and binocular (B)					M	B
Pupil size (photopic and under contrast sensitivity conditions)					X	X
Keratometry	X ^b				X	
Intraocular pressure	X		X	X	X	X
Biomicroscopic slit-lamp exam ^b	X		X	X	X	X
Dilated fundus exam with fundus visualization	X					X
Adverse events		X	X	X	X	X
Ocular medications	X	X	X	X	X	X
Ocular/visual symptoms (non-directed)	X		X	X	X	X
Subject questionnaires	X				X	X

^a With corneal stability check for contact lens wearers

^b Includes determination of medical and lens findings/complications

^c Monocular testing required for first-eye only

APPENDIX B EQUIPMENT LIST

The following equipment will be supplied to an investigative site for the duration of the study provided that the site does not already have such equipment available for use. This equipment loan will be documented in the Clinical Trial Agreement, which indicates that the equipment is to be returned to Abbott Medical Optics at the completion of the study.

- M&S Technologies CTS-1000 Smart System[®] Computerized Vision Testing System, including laptop computer, tablet, and glare bracket
- Good-Lite EVS-1500 retro-illuminated visual acuity light box and stand
- Four Good-Lite ETDRS near visual acuity charts (100% contrast) on two cards, for a test distance of 40 cm
- Neutral density trial frame lenses for mesopic testing
- +0.12 D trial frame lenses
- Gossen Light Meter
- Tape measure (meters)
- Colvard Pupillometer (if site does not use a NeurOptics pupillometer)
- AMO insertion systems:
 - ONE SERIES Ultra Implantation System with cartridges, or
 - UNFOLDER Platinum 1 Series Implantation System with cartridges

